### 11.2 Secondary Efficacy Analyses

#### 11.2.1 Duration of overall response

The duration of overall response is measured from the time measurement criteria are met for CR or PR (whichever is first recorded) until the first date that recurrent disease or PD is objectively documented (taking as reference for PD the smallest measurements recorded since the treatment started).

The duration of overall CR is measured from the time measurement criteria are first met for CR until the first date that recurrent disease is objectively documented.

The duration of overall response and the duration of overall CR will be summarized with Kaplan-meier methodology. Only patients with a PR and/or CR will be included in the summary.

The duration of response will be summarized for the both the investigator assessment and the independent radiology review.

## **11.3 Exploratory Endpoints**

### ***11.3.1 Change from Baseline in Sum of the Longest Diameters (SLD) of Target Lesions***

The largest decrease from baseline in the sum of the longest diameters (SLD) of target lesions will be displayed graphically for all patients and relevant subgroups using a waterfall plot.

### ***11.3.2 Time to Treatment Failure***

The time to treatment failure will be computed as 1+ the number of days from the first dose of study drug to the last dose of study drug.

The subgroup of patients that continue receiving study drug past an event of disease progression will be summarized separately.

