#### **5.1.4 Treatment Post-progression (Phase 1 and Phase 2)**

Patients may opt to continue to receive treatment with CO-1686 following radiographic progression as outlined in the NCCN guidelines for treatment of NSCLC with EGFR TKIs if patient provides additional consent, the investigator feels it is in the patient's best interest and with sponsor approval. In general, eligible patients may include those with asymptomatic systemic progression or locally symptomatic progression, such as brain metastases amenable to local treatment, with concomitant asymptomatic systemic progression or continued systemic disease control. This must be discussed with the sponsor and will be reviewed on a case-by-case basis.

If a patient continues treatment post-progression, all study assessments including safety assessments, efficacy assessments, QOL administration, and blood collection for biomarker analysis and exploratory research should continue per protocol and data should be captured in the

eCRF. The patient should be discontinued from treatment once it is clear that no further clinical benefit can be achieved.

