### **11.2.8 Time to Treatment Failure - Exploratory Endpoint**

The time to treatment failure will be computed as 1+ the number of days from the first dose of study drug to the last dose of study drug.

The subgroup of patients that continue receiving study drug past an event of disease progression will be summarized separately.

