### 2.2.3 Exploratory Objective(s)

The exploratory objectives of phase 2 of this study are:

- To evaluate clinical benefit of continued CO-1686 treatment following disease progression
- To explore the concordance of T790M detected in tumor versus that detected in blood

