## 10.3 Exploratory Efficacy Variables

Exploratory variables include:

- Time to treatment failure
- Concordance of the presence of T790M mutation in blood and tumor tissue samples

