### ***11.3.6 Duration of Treatment in Patients with a Response***

The duration of treatment in patients with at least one investigator assessment of CR or PR is defined as 1+ the number of days from the first dose of study drug to the last dose of study drug.

The duration of response will be summarized with Kaplan-meier methodology.

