### 15 SUMMARY OF CHANGES FROM PROTOCOL SPECIFIED ANALYSES

Due to the conditional/accelerated approval strategy, the initial MAA and NDA submission data sets will focus on the subset of patients treated at 625mg BID or 500mg BID and enrolled up to the 31st of December with data as of April 2015.

The following changes from the protocol specified analyses are contained in this SAP:

1. The patients with death before first post-baseline scan will be included in the ORR analysis with the category of 'Death before first post-baseline scan'. This means that the tumor evaluable population was changed to an efficacy analysis population including those with death before first scan
2. Clarified how ongoing patients are analyzed for ORR
3. Added the duration of treatment in patients with a CR or PR
4. PFS analyses are not included since the study is still ongoing
5. PRO analyses are not included since the study is still ongoing
6. Analyses of the time to adverse events that results in a dose reduction, interruption, or discontinuation of study drug are included.

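### Time to treatment failure runs from first dose to last dose, so it does not isolate treatment after progression, which is what its objective is about

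*SAP*

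**What the plan says.** Protocol Table 8 and the synopsis list Phase 2 objectives against endpoints. The exploratory objective, repeated in SAP 2.2.3, is "To evaluate clinical benefit of continued CO-1686 treatment following disease progression". The only endpoint beside it is time to treatment failure, which SAP 10.3 also lists as an exploratory efficacy variable.

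Protocol 11.2.8 and SAP 11.3.2 define that endpoint identically, as "computed as 1+ the number of days from the first dose of study drug to the last dose of study drug". Both then add one sentence: "The subgroup of patients that continue receiving study drug past an event of disease progression will be summarized separately". Neither section starts a clock at progression, names a failure event, or states what happens to patients still on drug at the data cutoff.

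Three other places bear on the point:

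- SAP 11.3.6 defines duration of treatment in responders by the same interval, which "is defined as 1+ the number of days from the first dose of study drug to the last dose of study drug".
- SAP Section 15 states that "PFS analyses are not included since the study is still ongoing".
- Protocol 5.1.4 sets the conditions for treatment past progression (additional consent, investigator judgement, sponsor approval) and says when it ends: "The patient should be discontinued from treatment once it is clear that no further clinical benefit can be achieved".

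**The concern.** The objective asks what patients gain from staying on drug once they have progressed, but the endpoint starts counting at first dose. In a continuing patient the reported number is a sum of two periods, and the plan never reports the second one alone. A subgroup that progressed late and stopped soon afterwards can show a longer time to treatment failure than a subgroup that progressed early and was treated for a long time after that. A reader given only the sum could take the first result as evidence for continuing the drug.

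What is at stake is modest. One stated exploratory objective would be reported with a number that does not address it.

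**Working it through.** The plan gives no expected value, event count or power for this endpoint, so there is no figure of its own to reproduce. The check is on the definition.

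**Decomposition.** Let F be the date of first dose, P the date of first progression and L the date of last dose. For a patient treated past progression:

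L − F + 1 = (P − F) + (L − P + 1)

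The left side is time to treatment failure as defined. The first term on the right is time to progression. The second is treatment time after progression, the only part relevant to the objective.

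**Same total, different content (assumed values).** Fix the total at 300 days.

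- Progression 42 days after first dose: 300 − 42 = 258 days after progression, 258/300 = 86%.
- Progression at 189 days: 300 − 189 = 111 days, 37%.
- Progression at 290 days: 300 − 290 = 10 days, 3%.

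**The ordering can reverse (assumed values).** Take independent exponential times before and after progression, and simulate the sum.

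- Medians of 90 days before and 120 days after: median sum about 253 days.
- Medians of 180 days before and 60 days after: median sum about 275 days.

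The second group has the longer time to treatment failure and half the median post-progression treatment.

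**How closely the sum tracks the relevant part (assumed values).** For independent exponential times the standard deviation is proportional to the median, so the correlation of the sum with its post-progression part is m_after / √(m_before² + m_after²).

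- 270 days before, 30 after: 30/√(270² + 30²) = 0.11.
- 90 days before, 120 after: 120/√(90² + 120²) = 120/150 = 0.80.

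The endpoint could be a poor or a fair guide to post-progression treatment, depending on values that the documents do not give.

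**Illustrative pre-progression share.** With assumed medians of 5 to 8 months before progression and 1.5 to 3 months after, the extremes are:

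- 5/(5 + 3) = 62.5%
- 8/(8 + 1.5) = 84%

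These are ratios of assumed medians, not estimates for this trial. The median of a sum is not the sum of the medians.

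**Does the subgroup sentence repair it?** It changes who is summarised and leaves F as the start. To be in the subgroup, a patient must also have stayed on drug until progression and been cleared to continue, so the first term is built into every value.

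**Can the reader recover the second term elsewhere?** Not from the analyses in this SAP, because PFS is omitted. Subtracting a whole-cohort median PFS would not give it for this subgroup in any case.

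**Patients still on drug.** SAP Section 3 and Protocol 11.2.1 apply Kaplan-Meier to time-to-event variables generally and call for the number censored. SAP 14.1 and 14.2 state a censoring date for time to first dose-modifying adverse event and time to first glucose-lowering medication. SAP 11.3.2 states none. The question will arise in practice: SAP 2.4 includes 500 mg and 625 mg BID patients enrolled to 31 December 2014 with a cutoff of 29 April 2015, which leaves the last enrolled 31 + 28 + 31 + 29 = 119 days of follow-up.

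**The case against.** The case against has several parts, and some of it stands.

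- **The documents do not show that most of the interval falls before progression.** A reader might infer this from the definition. However, the first scheduled scan is at the end of Cycle 2, so an early progressor who continues could have mostly post-progression time. The 86% to 3% spread above makes the same point. This stands: the endpoint mixes two periods in unknown proportion.
- **Censoring is largely covered.** A reader might take SAP 11.3.2 to count an ongoing patient's latest dose as a failure. The general Kaplan-Meier convention in SAP Section 3 and Protocol 11.2.1 does not support that reading. What remains is narrower: no rule for patients on drug at cutoff is written for this variable.
- **No comparison is planned.** Guaranteed time before progression distorts a contrast with patients who stopped, and the plan specifies no such contrast. A charge of biased comparison would go beyond the text. The separate summary still contains that time.
- **The replacement is also imperfect.** Time from progression to last dose has no comparator, and its patients are selected by consent, judgement and approval. It describes treatment duration and does not prove benefit. That is correct. But because Protocol 5.1.4 ties stopping to the end of benefit, it is at least a rough proxy over the right period.
- **The endpoint is exploratory,** with no alpha, power or decision attached. That limits the weight of the point but leaves the mismatch in place.

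**Conclusion.** The mismatch is real and of low impact. The sole endpoint for the post-progression objective is overall treatment duration under another name, and within this SAP nothing reports post-progression treatment time. A long value in the continuing subgroup may mean late progression, longer treatment afterwards, or both.

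The finding about the definition rests on the text alone. Its numerical size rests entirely on assumptions: the 62% to 84% range follows from assumed medians, and the documents contain no post-progression duration against which to test it. It would also go too far to say that the objective becomes fully answerable once the clock is moved, because the subgroup would still be selected and uncontrolled. Primary ORR and duration of response are unaffected.

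**What to change.** In SAP 11.3.2:

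- For patients treated past progression, add post-progression treatment duration = date of last dose − date of first investigator-assessed RECIST progression + 1. Use the same progression date to define membership of the subgroup, since both investigator and independent assessments exist.
- Summarise it by Kaplan-Meier under the convention in SAP Section 3, with patients still on drug at the data cutoff censored at that date.
- Keep the first-to-last-dose interval, label it overall treatment duration, and apply the same censoring rule.
- State that the new measure is descriptive, because the subgroup is selected and has no comparator.

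The cost is a few lines of SAP wording and one extra table. The dates are already collected: Protocol 11.2.4.2 uses the first progression date for patients who continue, and Protocol 5.1.4 requires post-progression data to be entered in the eCRF.

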### ***11.3.3 Concordance of the presence of T790M mutation in blood and tumor tissue samples***

An exploratory pharmacodynamic endpoint is the detection and quantification of mutant EGFR cell-free DNA in blood collected at baseline and with every tumor assessment. The presence of the T790M mutation at baseline and subsequent time points will be presented both with frequencies and percentages. In addition, the relationship between T790M detected in tumor compared with that detected in blood, and urine where applicable, will be explored. This will involve determining the sensitivity, specificity, positive and negative predictive values with 95% confidence intervals (CIs) of blood with respect to tumor.

### ***11.3.4 Detection of T790M in Urine Samples***

The frequency and percentage of Phase 1 patients with T790M present in urine samples will be presented for the subgroup of patients that provide samples.

### ***11.3.5 Metabolite Profiling***

The association between the key efficacy and safety parameters and the CO-1686 metabolite profile will be evaluated in the subset of patients with available metabolite pharmacokinetic data.

The metabolite PK parameters will be summarized for patients with and without an objective response of CR/PR. Similarly, the metabolite PK parameters will be summarized for patients with and without key adverse events, e.g., hyperglycemia and QTc prolongation.

### ***11.3.6 Duration of Treatment in Patients with a Response***

The duration of treatment in patients with at least one investigator assessment of CR or PR is defined as 1+ the number of days from the first dose of study drug to the last dose of study drug.

The duration of response will be summarized with Kaplan-meier methodology.

## **12 STATISTICAL/ANALYTICAL ISSUES**

### **12.1 Handling of Dropouts or Missing Data**

All available data will be used to the greatest extent possible without any imputations for missing data.

## 12.2 Pooling of Centers in Multi-Center Studies

The data from all study centers will be pooled for analysis.

## 12.3 Multiple Comparison/Multiplicity

No adjustments for multiple comparisons will be made.

## 12.4 Examination of Subgroups

Subgroup analyses of the key efficacy endpoints based upon the following variables may be performed for the safety and efficacy-evaluable populations:

1. T790M status
2. EGFR activating mutation
3. Method used for detecting T790M status
4. ECOG Performance Status
5. Age
6. Race
7. Gender
8. Presence of brain metastases at baseline
9. History of glucose intolerance.

## 12.5 Interim Analysis and Data Monitoring

No formal interim analyses are planned.

## 13 PHARMACOKINETICS / PHARMACODYNAMIC ANALYSIS

Pharmacokinetic (PK) parameters will be determined using noncompartmental methods. AUC from Time 0 to the last observation will be calculated using the trapezoid rule. The  $k_{el}$  will be calculated using log-linear regression on the terminal part of the concentration time curve. The terminal half-life and the AUC from the last observation to infinity will be calculated from the estimated  $k_{el}$ . Other parameters to be determined are  $AUC_{(0-t)}$ ,  $C_{trough}$ ,  $C_{max}$ ,  $T_{max}$ ,  $V_{ss}/F$ , and  $Cl/F$ .

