In the Study CO-1686-008, PK data following administration of the HBr salt formulation were available from a total of 44 patients (4 started at 500 mg BID, 10 switched from CO-1686 free base to 500 mg BID HBr, 15 started at 625 mg BID, 9 started at 750 mg BID, and 6 started at 1000 mg BID). CO-1686 HBr showed increased absorption and thus, higher exposure than free base. The median  $T_{max}$  was 2.5 to 3.25 hours and  $T_{1/2}$  ranged from 1.7 to 4.7 hours, which was slightly shorter than free base in the majority of patients in the  $\leq 750$  mg BID cohorts while the  $T_{1/2}$  was more similar to free base in the 1000 mg BID cohort. Following CO-1686 HBr administration, exposure (measured as  $C_{max}$  and  $AUC_{0-24}$ ) increased dose-proportionally from 500 mg to 1000 mg BID (Figure 4). Comparative PK were available in 8 patients who originally started CO-1686 treatment at 900 mg CO-1686 free base BID and then switched to 500 mg CO-1686 HBr BID. Results suggest that CO-1686 HBr delivered a higher exposure, assessed by  $C_{max}$ , and lower variability mainly due to a much improved absorption in patients who had low exposure when receiving free base (Figure 5).

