**Table 7: Phase 1 Primary, Secondary and Exploratory Objectives and Endpoints**

Phase 1	
Primary Objectives	Primary Endpoints
To evaluate the toxicity profile of escalating doses of CO-1686 and to determine the MTD and RP2D	The incidence of Grade 3 or 4 adverse events (AEs) and clinical laboratory abnormalities defined as dose-limiting toxicities (DLTs)
To characterize the PK profile of CO-1686	PK parameters including area under the curve from time zero to time t ( $AUC_{0-t}$ ), $AUC$ from time zero to infinity ( $AUC_{0-\infty}$ ), maximum concentration ( $C_{max}$ ), time to maximum concentration ( $T_{max}$ ), elimination half-life ( $T_{1/2}$ ), elimination rate constant ( $k_{el}$ ), volume of distribution at steady state after nonintravenous administration ( $V_{ss}/F$ ), and total plasma clearance ( $Cl/F$ ) for CO-1686
Secondary Objective	Secondary Endpoints
To characterize the PK profile of CO-1686 after a high-fat breakfast vs in the fasted state	PK parameters $C_{max}$ and $AUC$ for CO-1686 (fasted and fed)
To evaluate the effects of CO-1686 on the QT/QTc interval	Change from baseline in QT/QTc interval
To evaluate tumor response (overall response rate [ORR] + duration of response) of CO-1686	ORR and duration of response per Response Criteria in Solid Tumors (RECIST) Version 1.1
Exploratory Objectives	Exploratory Endpoints
To characterize lung-cancer and treatment-related symptoms in patients at baseline and in response to CO-1686 using the Dermatology Life Quality Index, the EORTC QLQ - LC13, and the EORTC QLQ-C30.	Change from baseline in patient-reported outcomes
To explore the concordance of T790M detected in tumor versus that detected in blood.	Concordance of the presence of T790M mutation in blood and tumor tissue samples
To determine if T790M is detectable in urine (optional sampling).	Detection of T790M in urine samples

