## 7.2 Method of Assigning Patients to Treatment Groups

All patients enrolled in the study will receive oral CO-1686. Patients in Phase 2 will receive one of 3 dose levels of CO-1686.

Phase 2 Cohorts A and B were initiated under Amendment 4 at a dose of 750 mg BID and are currently enrolling at this dose. As the Phase 1 efficacy data matured, the recommended dose was adjusted to 625 mg BID, and under Amendment 6, patients were no longer enrolled in the 750 mg BID dose level for Cohorts A and B, but were to be assigned by the sponsor to receive either 625 mg BID or 500 mg BID in Cohorts A and B. Patients who are already receiving 750 mg BID will continue at this dose. Amendment 6 also increased the size of cohorts A and B from up to approximately 40 patients each to approximately 190 patients each (up to approximately 75 patients per dose level of 500 mg BID and 625 mg BID, with up to approximately 40 patients for 750 mg BID), and created 1 additional cohort (Cohort C) with up to 100 patients. Amendment 7 allowed the sponsor to enroll the RP2D of 625 mg BID before the 500 mg BID dose in order to increase experience with the RP2D to support the ongoing Phase 2 and Phase 3 CO-1686 program. Note that, under Amendment 7, as allocation to dose level is not randomized, availability of the central T790M testing result will not be required before enrollment, so long as the following criteria are met:

- a. Have undergone a biopsy of either primary or metastatic tumor tissue within 60 days of dosing with study drug and have tissue available to send to the sponsor's lab or are able to undergo a biopsy during screening. No change (except for washout or dose adjustment if required to manage adverse effects) in antitumor therapy regimen is allowed between the biopsy and CO-1686 initiation (Study Inclusion Criterion 3);

AND

- b. Local positive T790M result from biopsy taken at same time as central testing biopsy, with results available for sponsor review before enrollment

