### **11.2.5 Pharmacokinetic Analyses – Secondary Endpoint**

As a primary endpoint in Phase 1 and a secondary endpoint in Phase 2 of the study, PK parameters will be determined using noncompartmental methods. AUC from Time 0 to the last

observation will be calculated using the trapezoid rule. The  $k_{el}$  will be calculated using log-linear regression on the terminal part of the concentration time curve. The terminal half-life and the AUC from the last observation to infinity will be calculated from the estimated  $k_{el}$ . Other parameters to be determined are  $C_{max}$ ,  $T_{max}$ ,  $V_{ss}/F$ , and  $Cl/F$ .

As a secondary endpoint in Phase 1, the effect of food on PK parameters including, but not limited to,  $C_{max}$  and AUC, will be compared using analysis of variance (ANOVA) techniques.

As a secondary endpoint in Phase 2, additional plasma samples will be collected on Day 15 from a minimum of three patients enrolled at the RP2D. Individual pooled plasma samples, one from each of these patients, will be prepared using the method proposed by Hamilton. The pooled plasma samples will be further processed before being analyzed by high-performance liquid chromatography coupled in-line with ultraviolet spectrophotometric and tandem mass spectrometric detection (HPLC-UV-MS/MS).

A specific population PK data analysis plan will be developed and will outline the detailed approach to data handling, model development and diagnostics, individual model parameter estimation, exploration of covariate effects, and final model evaluation techniques.

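### Vss/F is listed as a noncompartmental parameter, but oral-only data cannot give a steady-state volume that way; relabel it Vz/F or take it from the population PK model (minor)

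*SAP*

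**What the plan says.** SAP section 13 opens with "Pharmacokinetic (PK) parameters will be determined using noncompartmental methods". It gives a method for AUC, for kel ("log-linear regression on the terminal part of the concentration time curve"), for half-life and for the AUC extrapolation. It then continues "Other parameters to be determined are", followed by a list that contains Vss/F and Cl/F. Protocol 11.2.5 has the same structure ("PK parameters will be determined using noncompartmental methods") and again lists Vss/F without a formula.

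Protocol Table 7 puts Vss/F among the Phase 1 primary PK endpoints and defines it as "volume of distribution at steady state after nonintravenous administration". It also appears in the synopsis and in 9.8.3.2. Neither section mentions the first-moment area (AUMC), mean residence time or mean absorption time.

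Protocol 7.2 states the route: "All patients enrolled in the study will receive oral CO-1686". No intravenous dose is given in this study. Protocol 11.2.5 separately promises a population PK analysis plan, which is not among the documents reviewed.

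**The concern.** A noncompartmental steady-state volume is clearance multiplied by the mean residence time of drug once it is in the circulation. After an intravenous bolus, AUMC/AUC measures that time directly. After an oral dose, AUMC/AUC also includes the mean time spent being absorbed. Separating the two requires intravenous data or a model of absorption. Denser sampling does not help, because this is a matter of identifiability and not of precision.

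The plan therefore names a parameter that its stated method cannot deliver, and only two practical readings remain:

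- **Cl/F times oral residence time.** This overstates the volume by an amount that depends on absorption.
- **(Cl/F)/kel.** This is the terminal-phase volume Vz/F, reported under another parameter's name.

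The first reading matters here because protocol 3.4.2 reports that a high-fat meal delayed Tmax in most subjects with no change in half-life, for both free base and HBr. Under that reading, a change in absorption alone would appear in the tables as a change in volume.

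**Working it through.** The documents state no volume, residence time, absorption time or ka, so there is no figure of theirs to reproduce. The check asks how large the excess would be under the first reading.

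**Inputs, protocol 3.4.2**
- HBr: median Tmax "was 2.5 to 3.25 hours"; half-life "ranged from 1.7 to 4.7 hours".
- Free base: Tmax 1.5 to 4 h; half-life 3.5 to 5.5 h.

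**Assumptions, not in the documents**
- One compartment, first-order absorption, no lag, ka ≥ ke.
- Vss/F computed as Cl/F × oral MRT with nothing subtracted.
- A half-life of 3.0 h, used as an illustrative value inside the HBr range.

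**Formulas**
1. MRT(oral) = MRT(disposition) + MAT, so Cl/F × MRT(oral) exceeds Vss/F by the fraction MAT / MRT(disposition).
2. In this model MRT(disposition) = 1/ke and MAT = 1/ka. The excess is q = ke/ka.
3. ke = ln 2 / half-life, and Tmax = ln(ka/ke)/(ka − ke). Rearranged: ke × Tmax = q ln(1/q)/(1 − q), solved for q.

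| Form | Half-life (h) | Tmax (h) | 1/ke (h) | ke × Tmax | MAT (h) | Excess q |
|---|---|---|---|---|---|---|
| HBr | 4.7 | 2.5 | 6.78 | 0.369 | 1.18 | 17.4% |
| HBr | 4.7 | 3.25 | 6.78 | 0.479 | 1.80 | 26.5% |
| HBr | 3.0 | 2.5 | 4.33 | 0.578 | 1.57 | 36.3% |
| HBr | 3.0 | 3.25 | 4.33 | 0.751 | 2.50 | 57.8% |
| HBr | 1.7 | 2.5 | 2.45 | 1.019 | – | no solution |
| HBr | 1.7 | 3.25 | 2.45 | 1.325 | – | no solution |
| Free base | 5.5 | 1.5 | 7.93 | 0.189 | 0.51 | 6.5% |
| Free base | 5.5 | 4 | 7.93 | 0.504 | 2.29 | 28.9% |
| Free base | 3.5 | 1.5 | 5.05 | 0.297 | 0.63 | 12.5% |
| Free base | 3.5 | 4 | 5.05 | 0.792 | 3.22 | 63.8% |

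**The 1.7 h rows.** The right-hand side of step 3 rises from 0 to 1 as q goes from 0 to 1, so the model allows Tmax no later than 1/ke. At a half-life of 1.7 h that limit is 2.45 h, and both reported Tmax values lie beyond it.

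**Lag time.** With an assumed lag of 0.25, 0.5 or 1.0 h, the 17.4% case (half-life 4.7 h, Tmax 2.5 h) becomes 18.5%, 19.7% or 22.8%.

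**Numerical check.** Integrating the concentration curve for half-life 4.7 h and Tmax 2.5 h with a true volume of 100 gives Cl/F × MRT(oral) = 117.4 and (Cl/F)/kel = 100.0. In this model the second formula carries no absorption bias. It is still a terminal volume. The agreement with Vss arises because a one-compartment model has only one volume.

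**The case against.** The strongest reply is that the size of the bias rests on a formula the plan never states. If the analyst computes (Cl/F)/kel from two quantities already planned, the absorption bias in the model above is zero and only a label is wrong. That is correct, and it is why the percentages are conditional. It does not remove the point: a quantity defined in the protocol as a steady-state volume would still be something else.

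A reader might infer that the reported volume will be inflated by 17% to 100%. The documents do not support that. The lower figure ignores free base, which goes down to 6.5%. The upper figure is the ceiling of the model at ka = ke, and the 1.7 h half-life that suggests it does not fit the model at either reported Tmax.

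The inputs are also loosely matched. Protocol 3.4.2 gives a range of median Tmax values and, separately, a range of half-lives, without saying which belong together.

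A reader might also infer that the food, formulation or dose comparisons are compromised. The food-effect endpoint in Table 7 is Cmax and AUC. Protocol 11.2.5 leaves room for other parameters but does not name volume. The formulation and dose comparisons described in 3.4.2 rest on Cmax and AUC. No planned comparison of volume is stated.

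Finally, the population PK analysis could supply a model-based volume. It may well do so, but its plan cannot be judged here, and its existence does not correct the noncompartmental list.

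**Conclusion.** The point holds as a mismatch between a named parameter and its method. With oral dosing only, Vss/F cannot be obtained noncompartmentally, so the reported value would be either biased upward or mislabelled.

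Under the first reading and the stated assumptions, the excess is about 17–27% for HBr at a half-life of 4.7 h, 36–58% at the illustrative 3.0 h, and about 6–64% for free base. No figure can be given at 1.7 h. These are indications of scale for assumed pairings, not estimates for this study's patients. Under the second reading the error is in the name.

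Vss/F belongs to the Phase 1 primary PK set, but it is descriptive. No efficacy, DLT or sample-size result depends on it, and no dose decision is shown to use it. This is a minor correction.

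**What to change.** In SAP section 13, protocol 11.2.5, 9.8.3.2, Table 7 and the synopsis, replace Vss/F with Vz/F and state the formula, Vz/F = (Cl/F)/kel. Label it an apparent terminal-phase volume.

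Add one caveat: if absorption is slower than elimination, the terminal slope reflects ka and not ke, so Vz/F then depends on absorption as well.

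If a steady-state volume is wanted, report the apparent volume from the population PK model already planned, and say so in that plan.

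The cost is a few lines of text. Cl/F and kel are already planned, and no sampling, assay or visit changes.
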